### 7.3 Liver safety monitoring

To ensure patient safety and enhance reliability in determining the hepatotoxic potential of an investigational drug, a standardized process for identification, monitoring and evaluation of liver events will be followed for pediatric subjects. The liver safety monitoring procedure is applicable until the subject reaches adulthood. Once a subject reaches adulthood ( $\geq 18$  years of age) this procedure no longer needs to be followed. However, if a subject is followed up for a specific event with liver monitoring procedures while turning 18, follow-up should continue until the event stabilizes or resolves.

The following two categories of abnormalities / adverse events have to be considered during the course of the study:

- Liver laboratory triggers, which will require repeated assessments of the abnormal laboratory parameter
- Liver events, which will require close observation, follow-up monitoring and completion of the standard base liver CRF pages

Please refer to [Table 14-1](#) in [Appendix 2](#) for complete definitions of liver laboratory triggers and liver events.

Every liver laboratory trigger or liver event as defined in [Table 14-1 of Appendix 2](#) should be followed up by the investigator or designated personal at the trial site as summarized below. Detailed information is outlined in [Table 14-2 of Appendix 2](#).

For the liver laboratory trigger:

- Repeating the LFT within the next week to confirm elevation.

These LFT repeats should be performed using the central laboratory if possible. If this is not possible, then the repeats can be performed at a local laboratory to monitor the safety of the patient. Repeats laboratory should then be performed at central laboratory as soon as possible. If a liver event is subsequently reported, any local LFTs previously conducted that are associated with this event should be reported on the Liver CRF pages.

- If the elevation is confirmed, close observation of the patient will be initiated, including consideration of treatment interruption if deemed appropriate.

For the liver events:

- Repeating the LFT to confirm elevation as appropriate
- Discontinuation of the investigational drug if appropriate
- Hospitalization of the patient if appropriate
- A causality assessment of the liver event via exclusion of alternative causes (e.g., disease, co-medications)
- An investigation of the liver event which needs to be followed until resolution.

These investigations can include serology tests, imaging and pathology assessments, hepatologist's consultancy, based on investigator's discretion. All follow-up information, and

the procedures performed should be recorded on appropriate CRF pages, including the liver event overview CRF pages.

## **7.4 Renal safety monitoring**

To ensure patient safety and enhance reliability in determining the nephrotoxic potential of an investigational drug, a standardized process for identification, monitoring and evaluation of renal events will be followed for pediatric subjects. The renal safety monitoring procedure is applicable until the subject reaches adulthood. Once a subject reaches adulthood ( $\geq 18$  years of age) this procedure no longer needs to be followed. However, if a subject is followed up for a specific event with renal monitoring procedures while turning 18, follow-up should continue until the event stabilizes or resolves.

The following two categories of renal adverse events have to be considered during the course of the study:

1. Serum event:

- confirmed decrease in estimated glomerular filtration rate (eGFR) of  $\geq 25\%$  compared to baseline during normal hydration status as estimated by Schwartz equation :  
$$\text{eGFR (ml/min/1.73m}^2\text{)} = 0.413 \times \text{height (cm)} / \text{serum creatinine (mg/dl)}$$

2. Urine event: New onset ( $\geq 1+$ ) proteinuria, hematuria or glucosuria

- new onset of proteinuria should be confirmed by urinary protein creatinine ratio

Every renal laboratory trigger or renal event as defined in [Table 7-1](#) should be followed up by the investigator or designated personnel at the trial site as summarized below.

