**Table 7-1 Specific Renal Alert Criteria and Actions**

Serum Event	
Estimated GFR decrease 25 – <50% compared to baseline and eGFR <90mL/min/1.73m 	Confirm  25%‐<50% decrease and eGFR <90mL/min/1.73m  after 24‐48h, if possible. If it persists  follow up with repeat, if possible, within 2‐5 days and perform urinary PCR on a first morning urine collection. Then do some frequent monitoring (preferably weekly) until event resolves  or stabilizes  . If event does not resolve or stabilize consider consulting nephrologist and/or drug interruption.
Acute Kidney Injury: Serum Estimated GFR decrease ≥ 50 % compared to baseline	Follow up within 24‐48h if possible. If value persists, consider consulting nephrologist and/or drug interruption.
Urine Event	
New dipstick proteinuria ≥ 1+	Confirm  value after 24‐48h, if possible. If dipstick value confirmed: a) perform  urinary protein creatinine ratio (PCR) within 2‐5 days, if possible, on a first morning urine collection. b) perform urine microscopy and evaluate. If PCR > 0.2 g/g and/or urine microscopy has findings (e.g. crystals, casts, dysmorphic RBC, leukocytes) consider consulting nephrologist or drug interruption or discontinuation.
New dipstick glucosuria ≥ 1+ not due to diabetes	Confirm value after 24‐48h, if possible. If it persists: a) perform, blood glucose (fasting). b) perform urinary protein/creatinine ratio. If PCR ratio > 0.2 g/g and blood glucose normal consider consulting nephrologist and /or drug interruption or discontinuation.
New dipstick hematuria ≥ 1+ not due to trauma or menses	Confirm  value after 24‐48h, if possible. If it persists: a) perform  urinary protein creatinine ratio (PCR) within 2‐5 days if possible, on a first morning urine collection. b) perform urine microscopy and evaluate. If PCR > 0.2 g/g and /or urine microscopy has findings (e.g. crystals, casts , dysmorphic RBC, leukocytes) consider consulting nephrologist or drug interruption or discontinuation.
For all renal events:	

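### Protocol Section 7.4 defines the renal serum event by two thresholds that disagree when baseline eGFR is 120 or higher, and the SAP does not say which one is counted

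*Protocol*

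**What the plan says.** Protocol Section 7.4 opens its list with "The following two categories of renal adverse events have to be considered during the course of the study". Item 1, the serum event, is a "confirmed decrease in estimated glomerular filtration rate (eGFR) of" at least 25%, "compared to baseline during normal hydration status as estimated by Schwartz equation". No absolute eGFR level appears there.

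The same section then directs follow-up to "Every renal laboratory trigger or renal event as defined in" Table 7-1, which is titled "Specific Renal Alert Criteria and Actions". Under its own serum event heading the table has two rows:

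- **Milder row.** A fall of 25% to below 50% "compared to baseline and eGFR <90mL/min/1.73m"². One action is "perform urinary PCR on a first morning urine collection".
- **Acute kidney injury row.** A fall of 50% or more, with no absolute limit. The actions are follow-up within 24 to 48 hours and then "If value persists, consider consulting nephrologist and/or drug interruption". The urinary protein/creatinine ratio (PCR) is not named.

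The block at the foot of the table asks sites to document contributing factors in the CRF for all renal events. Protocol Section 6.5.5.3 makes quantitative urinalysis, including PCR, mandatory whenever an eGFR fall reaches an alert value of Section 7.4. SAP Section 2.9.3.2 plans a summary table and a listing for a renal event overview, without a criterion for what counts as an event.

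**The concern.** One section defines one named safety event twice, with different limits. A site that works from the text records a renal event for a child whom a site working from the table does not record. Section 7.4 describes the process as standardized, and the SAP tabulates the result, so the count depends on which paragraph the site followed.

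Nothing else in the documents settles the matter. SAP Table 2-13 grades eGFR by absolute level, so it does not say whether a given fall from baseline is a renal event. The liver analyses, by contrast, have explicit criteria (SAP Table 2-14).

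There is a second, smaller point. The most severe serum row is the only row of Table 7-1 that does not name PCR, so the action table and Section 6.5.5.3 do not match there.

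**Working it through.** The plan states no figure to reproduce. The check compares the two rules for a confirmed value in normal hydration.

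**Inputs**

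- B = baseline eGFR, the average of the values before first dose (Protocol 6.5.5.2, Estimated GFR).
- E = later eGFR. Fall = 1 − E/B.
- Text rule (7.4, item 1): fall ≥ 25%, that is E ≤ 0.75B.
- Table rule (Table 7-1): fall 25% to <50% and E < 90, or fall ≥ 50%, that is E ≤ 0.5B.

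**Direction.** Both table rows require a fall of at least 25%. Every table event is therefore a text event, and disagreement can only mean text yes, table no.

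**Zone of disagreement.** This needs E ≤ 0.75B, E ≥ 90 and E > 0.5B together.

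- It exists only if 0.75B ≥ 90, so B ≥ 120. At B = 110, 0.75B = 82.5 and the zone is empty.
- For B from 120 to below 180, the zone is 90 ≤ E ≤ 0.75B.
- For B ≥ 180, 0.5B ≥ 90, so the acute kidney injury row takes the lower part and the zone is 0.5B < E ≤ 0.75B.

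| Baseline B | Zone for E | Falls in the zone |
|---|---|---|
| 110 | none | none |
| 120 | 90 only | 25% |
| 130 | 90 to 97.5 | 25% to 1 − 90/130 = 30.8% |
| 140 | 90 to 105 | 25% to 1 − 90/140 = 35.7% |
| 150 | 90 to 112.5 | 25% to 1 − 90/150 = 40.0% |
| 200 | above 100 to 150 | 25% to just under 50% |

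**Two examples.** From 140 to 100 the fall is 1 − 100/140 = 28.6%: an event in the text, in no row of the table. From 200 to 95 the fall is 1 − 95/200 = 52.5%: an event under both rules, although E is above 90.

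**What this means in creatinine.** With the protocol's Schwartz formula and an assumed height of 150 cm, 0.413 × 150 = 61.95. An eGFR of 140 is then 61.95/140 = 0.44 mg/dL and an eGFR of 100 is 61.95/100 = 0.62 mg/dL. A baseline of 120 corresponds to 61.95/120 = 0.52 mg/dL.

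**PCR by row of Table 7-1.** Milder eGFR row: yes. Acute kidney injury row: no. Proteinuria: yes. Glucosuria: yes. Hematuria: yes. Four of five rows name it.

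**The case against.** The best defence is that the text is an overview and the table holds the detail. Section 7.3 on liver safety has the same shape: two categories, then a table. For follow-up this is right. Section 7.4 sends follow-up to the table, only the table is titled as alert criteria, and its footnote 3 treats an eGFR above 90 as stabilized. Table 7-1 is therefore the better reading for repeat tests and PCR. It does not rescue the event label. Section 7.3 gives no thresholds in its text and refers to Table 14-1 for the full definitions, whereas Section 7.4 states a numerical threshold of its own.

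The second defence is that the label does little. Protocol Section 7.1 treats an abnormal laboratory value as an adverse event only if it causes signs or symptoms, is clinically significant or needs therapy. The heading in Section 7.4 does not by itself make a fall from 140 to 100 a reportable adverse event. SAP Section 2.9.3 also keeps such falls in the listings and change-from-baseline summaries. This stands, and it limits the size of the point.

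Third, the PCR in the acute kidney injury row is already ordered by Section 6.5.5.3. That also stands: silence in one row does not cancel a mandatory instruction elsewhere, so naming PCR there only brings the table into line.

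Fourth, the documents do not show that the narrower definition is clinically safer than the wider one. That is fair. Either definition, used alone, would remove the conflict. The table's is preferred because Section 7.4 already ties follow-up to it.

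A reader might also infer that the glucosuria row is wrong because it lists no microscopy, although Section 6.5.5.3 names glucosuria. The documents do not support this. That sentence orders microscopy as indicated in Section 7.4, and Table 7-1 gives glucosuria its own work-up of fasting glucose and PCR.

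**Conclusion.** The inconsistency is real and small. Section 7.4 states the serum event threshold in two incompatible ways. They classify a child differently only at baseline eGFR of 120 or higher, for values from 90 (or just above half of baseline once baseline reaches 180) up to 75% of baseline. What is affected is the renal event label, its CRF documentation and the count in SAP Section 2.9.3.2. The result rests on reading both statements literally. The documents give no eGFR distribution, so the number of children in the zone is unknown.

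Two stronger conclusions do not follow.

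- **Forced discontinuation.** Protocol Section 5.5.9 lists requirements met for renal events among the reasons to stop treatment, so a reader might infer that a child in the zone would have to stop. Table 7-1 only asks the investigator to consider interruption or discontinuation, and a child in the zone meets no serum row of it.
- **Never resolved.** A value in the zone is at most 0.75B, so it cannot be within 20% of baseline (0.80B), and a reader might infer that such an event can never count as resolved. Footnote 2 of Table 7-1 has an alternative limb, PCR below 0.2 g/g, which such a child can meet.

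**What to change.** 1. **Protocol 7.4, item 1.** Use the table's limits: *a confirmed fall in Schwartz eGFR, in normal hydration, either of 25% to below 50% from baseline with eGFR under 90 mL/min/1.73m², or of 50% or more from baseline.* The 24 to 48 hour follow-up in the acute kidney injury row still starts on the first value.
2. **Protocol Table 7-1, acute kidney injury row.** Add the instruction already used in the milder row, "perform urinary PCR on a first morning urine collection". Section 6.5.5.3 stays as it is.
3. **SAP 2.9.3.2.** Add: *serum renal events are counted by the rows of Table 7-1; falls of 25% to below 50% that leave eGFR at or above 90 are listed only.* The fall from 200 to 95 is then counted once, in the acute kidney injury row.

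The cost is two wording edits in the protocol and one sentence in the SAP. The second edit orders nothing new, and the central laboratory already reports eGFR with every serum creatinine. The downside is that falls of 25% to below 50% that stay at or above 90 lose the renal event label; they remain in the laboratory listings and change-from-baseline summaries.

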**Table 7-1 Specific Renal Alert Criteria and Actions**

Serum Event	
Estimated GFR decrease 25 – <50% compared to baseline and eGFR <90mL/min/1.73m 	Confirm  25%‐<50% decrease and eGFR <90mL/min/1.73m  after 24‐48h, if possible. If it persists  follow up with repeat, if possible, within 2‐5 days and perform urinary PCR on a first morning urine collection. Then do some frequent monitoring (preferably weekly) until event resolves  or stabilizes  . If event does not resolve or stabilize consider consulting nephrologist and/or drug interruption.
Acute Kidney Injury: Serum Estimated GFR decrease ≥ 50 % compared to baseline	Follow up within 24‐48h if possible. If value persists, consider consulting nephrologist and/or drug interruption.
Urine Event	
New dipstick proteinuria ≥ 1+	Confirm  value after 24‐48h, if possible. If dipstick value confirmed: a) perform  urinary protein creatinine ratio (PCR) within 2‐5 days, if possible, on a first morning urine collection. b) perform urine microscopy and evaluate. If PCR > 0.2 g/g and/or urine microscopy has findings (e.g. crystals, casts, dysmorphic RBC, leukocytes) consider consulting nephrologist or drug interruption or discontinuation.
New dipstick glucosuria ≥ 1+ not due to diabetes	Confirm value after 24‐48h, if possible. If it persists: a) perform, blood glucose (fasting). b) perform urinary protein/creatinine ratio. If PCR ratio > 0.2 g/g and blood glucose normal consider consulting nephrologist and /or drug interruption or discontinuation.
New dipstick hematuria ≥ 1+ not due to trauma or menses	Confirm  value after 24‐48h, if possible. If it persists: a) perform  urinary protein creatinine ratio (PCR) within 2‐5 days if possible, on a first morning urine collection. b) perform urine microscopy and evaluate. If PCR > 0.2 g/g and /or urine microscopy has findings (e.g. crystals, casts , dysmorphic RBC, leukocytes) consider consulting nephrologist or drug interruption or discontinuation.
For all renal events:	

Urine samples for testing for renal monitoring, and particularly those for the PCR ratio determination, must be collected at the first morning void.
 
Document contributing factors in the CRF: co-medication, other co-morbid conditions, and additional diagnostic procedures performed
 
Investigator and subject may decide to perform urinary PCR already with the first repeat
 
Monitor patient regularly (frequency at investigator's discretion) until either:
 
Event resolution: estimated GFR within 20% of baseline and >90mL/min/1.73m^2 or PCR < 0.2 g/g (<22.6 mg/mmol).
 
Event stabilization: estimated GFR within 20% of baseline OR >90mL/min/1.73m^2 or PCR < 0.3 g/g (<34 mg/mmol).
	

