**Table 6-2 Visit and Assessment schedule for the Extended treatment epoch**

Epoch	Extension Treatment Epoch																Follow-up Epoch				Unscheduled a
Visit	21	22	23	24	25	26	27	28	29	30	31	32	33	34	35	End of ext. treat. (EOT) b	F4 c	F8 c	F12 c	F16 c EOF	
Week	52 a	64	76	88	104	116	128	140	156	168	180	192	208	220	232	236	240	244	248	252	
Day	365	449	533	617	729	813	897	981	1093	1177	1261	1345	1457	1541	1625	1653	1681	1709	1737	1765	
Concomitant medications 		x	x	x	x	x	x	x	x	x	x	x	x	x	x	x	x	x	x		
Surgeries and non-drug procedures		x	x	x	x	x	x	x	x	x	x	x	x	x	x	x	x	x	x		
Physical Exam		s	s	s	s	s	s	s	s	s	s	s	s	s	s		s		s		
Height 		x	x	x	x	x	x	x	x	x	x	x	x	x	x		x		x		
Weight		x	x	x	x	x	x	x	x	x	x	x	x	x	x		x		x		
Vital signs (BP & pulse)		x	x	x	x	x	x	x	x	x	x	x	x	x	x	x	x	x	x		
Hematology 		x	x	x	x	x	x	x	x	x	x	x	x	x	x	x	x		x	x	
Blood Chemistry  , Urinalysis (local)		x	x	x	x	x	x	x	x	x	x	x	x	x	x	x	x	x	x		
Renal monitoring  (conditional) Urinalysis  , Urine Microscopy  , Fasting Glucose 		x	x	x	x	x	x	x	x	x	x	x	x	x	x	x	x	x	x		

Epoch	Extension Treatment Epoch																Follow-up Epoch				Unscheduled d
	21	22	23	24	25	26	27	28	29	30	31	32	33	34	35	End of ext. treat. (EOT) b	F4 c	F8 c	F12 c	F16 c EOF	
Visit	21	64	76	88	104	116	128	140	156	168	180	192	208	220	232	236	240	244	248	252	d
Week	52 a																				
Day	365	449	533	617	729	813	897	981	1093	1177	1261	1345	1457	1541	1625	1653	1681	1709	1737	1765 	Pregnancy test (in females of childbearing potential) 		x	x	x	x	x	x	x	x	x	x	x	x	x	x	x			x	x 	ECG (standard 12-lead)					x		x		x		x		x		x		x		x	x 	PASI		x	x	x	x	x	x	x	x	x	x	x	x	x	x	x	x	x	x	x 	IGA mod 2011		x	x	x	x	x	x	x	x	x	x	x	x	x	x	x	x	x	x	x 	CDLQI		x	x	x	x	x	x	x	x	x	x	x	x	x	x	x				x 	Adverse event assessment		x	x	x	x	x	x	x	x	x	x	x	x	x	x	x	x	x	x	x 	SAE assessment		x	x	x	x	x	x	x	x	x	x	x	x	x	x	x	x	x	x	x 	Data entry of weight into IRT 	x	x	x	x	x	x	x	x	x	x	x	x	x	x	x						
Contact IVRS/IWRS	x	x	x	x	x	x	x	x	x	x	x	x	x	x	x	x					

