glucose analysis by the central lab may also be required based on the glucose urine dipstick result. Once a subject reaches adulthood ( $\geq 18$  years of age) this procedure no longer needs to be followed.

[REDACTED]

 Serum pregnancy tests will be performed at screening and urine pregnancy test at all other scheduled visits. If there is a positive urine pregnancy test, study treatment must be withheld and a serum pregnancy test done at the same visit. Pregnancy tests will be performed in female subjects of child bearing potential, that is those who have started menstruation and/or are of age 12 or older.

[REDACTED]

 For every visit weight measured at that visit will be entered into IRT

 Secukinumab will be dispensed at site visits. In the extension treatment epoch, between site visits, it will be administered every 4 weeks at home, either by subject (self-injection only for adolescents of at least 12 years of age and under supervision) or by caregiver. In case subject or parent does not feel confident in performing home administrations they will be allowed to continue to perform administration at site. These administrations should occur at Wk 56, Wk 60, Wk 68, Wk 72, Wk 80, Wk 84, Wk 92, Wk 96, Wk 100, Wk 108, Wk 112, Wk 120, Wk 124, Wk 132, Wk 136, Wk 144, Wk 148, Wk 152, Wk 160, Wk 164, Wk 172, Wk 176, wk 184, Wk 188, Wk 196, Wk 200, Wk 204, Wk 212, Wk 216, Wk 224 and Wk 228.

[REDACTED]

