##### **Quantitative Urinalysis (conditional) and Urine Microscopy (conditional)**

If the dipstick result is positive for protein, glucosuria and/or blood, a urine sample will be sent to central laboratory for microscopic analysis which will include WBC, RBC, crystals, casts as indicated in the renal safety section ([Section 7.4](#)).

[figure not shown]
Furthermore, whenever eGFR decrease meets alert values as indicated in renal safety section ([Section 7.4](#)) a urine sample must be sent to the central laboratory for quantitative urinalysis. This analysis will include protein and creatinine to calculate the protein over creatinine ratio (PCR) and other parameters like bilirubin, blood, color, glucose, ketones, leukocytes, esterase, nitrite, pH, protein, specific gravity, urobilinogen.

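### Protocol Table 7-1, footnotes 2 and 3: an unassigned 'or' lets a normal urinary PCR close a persisting eGFR fall (wrong as written, minor)

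*Protocol*

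**What the plan says.** Protocol Section 7.4 defines two kinds of renal event: a serum event (a confirmed eGFR fall of at least 25%) and a urine event (new proteinuria, hematuria or glucosuria). It says that new proteinuria is to be confirmed by PCR.

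For a fall of 25 to less than 50% with eGFR below 90, Table 7-1 asks for confirmation and, if the fall persists, a repeat within 2 to 5 days with a first-morning PCR. The row continues: "Then do some frequent monitoring (preferably weekly) until event resolves" (footnote 2) or stabilizes (footnote 3). It ends: "If event does not resolve or stabilize consider consulting nephrologist and/or drug interruption".

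The footnotes stand under the heading for all renal events. Footnote 2 reads "Event resolution: estimated GFR within 20% of baseline and >90mL/min/1.73m 2 or PCR < 0.2 g/g". Footnote 3 begins "Event stabilization: estimated GFR within 20% of baseline OR", then gives eGFR above 90, then adds PCR below 0.3 g/g after another 'or'. In the text available, markers 2 and 3 appear only in the serum row just described.

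Section 6.5.5.3 separately requires a central quantitative urinalysis "whenever eGFR decrease meets alert values as indicated in renal safety section". It says: "This analysis will include protein and creatinine to calculate the protein over creatinine ratio (PCR").

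Section 7.4 stops the renal procedure at age 18, except that a subject already being followed for an event continues until it stabilizes or resolves. SAP Section 2.9.3.2 plans a renal event overview table and listings, and does not define closure.

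**The concern.** A PCR criterion is a natural end-point for proteinuria. It says little about whether a fallen eGFR has recovered, yet the footnotes offer it as an alternative in the one row where eGFR is the problem. The PCR should also be on hand in every such case, because both the serum row and Section 6.5.5.3 order it. A child with a persisting fall and little proteinuria would therefore meet a stated stopping rule at about the time monitoring is meant to begin.

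Three things hang on closure: the preferably weekly checks, the prompt to consider a nephrologist or interruption (which applies only if the event neither resolves nor stabilizes), and continued renal follow-up past the 18th birthday. Section 7.4 promises a standardized process, but two sites could record the same child as resolved and as ongoing.

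**Working it through.** The plan gives no figure to reproduce. The check is to evaluate the footnotes as logical rules on subjects who still meet the serum alert.

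**Inputs (Table 7-1).** Let b be baseline eGFR and g current eGFR.

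- Alert: 0.25 ≤ (b − g)/b < 0.50 and g < 90
- A: g within 20% of b
- B: g > 90
- C: PCR < 0.2 g/g
- D: PCR < 0.3 g/g

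**Rules.**

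- Footnote 2, literal: (A and B) or C
- Footnote 2, other grouping: A and (B or C)
- Footnote 3: A or B or D. Every connective is 'or', so grouping makes no difference.

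**Reduction.** While the alert is met, a fall of at least 25% makes A false, and eGFR below 90 makes B false. Therefore:

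- Footnote 2, literal, reduces to C: resolved exactly when PCR < 0.2.
- Footnote 2, other grouping, is never met.
- Footnote 3 reduces to D: stabilized exactly when PCR < 0.3.

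The eGFR parts can never close an event that still meets the alert. This follows from the definitions and needs no simulation. Any such closure comes from the PCR clause.

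**Illustration.** The values are mine, not from the documents. With b = 120, being within 20% requires g ≥ 0.8 × 120 = 96. At g = 72 the fall is (120 − 72)/120 = 40%, so the alert is met. At g = 100 the fall is 20/120 = 16.7%, so it is not.

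| g | PCR (g/g) | Alert met | Footnote 2, literal | Footnote 2, other grouping | Footnote 3 | eGFR criteria only |
|---|---|---|---|---|---|---|
| 72 | 0.10 | yes | resolved | no | stabilized | open |
| 72 | 0.25 | yes | no | no | stabilized | open |
| 72 | 0.50 | yes | no | no | no | open |
| 100 | 0.50 | no | resolved | resolved | stabilized | resolved |

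The first two rows show the defect. Regrouping footnote 2 does not cure it, because monitoring stops at either end-point and footnote 3 still supplies one. The last row shows that eGFR criteria alone close an event that has recovered.

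**Age 18.** Treatment runs to Week 236, and 236/52.2 is about 4.5 years. Secukinumab subjects aged about 18 − 4.5 = 13.5 or more at randomization who stay on treatment turn 18 before it ends. If PCR closes such a subject's event after the birthday, Section 7.4 does not require the renal procedure for a later low eGFR. How many subjects would have an open event at that moment cannot be derived.

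**The case against.** The strongest reply is that nobody would read the table this way. Section 7.4 ties the serum event to eGFR and the confirmation of proteinuria to PCR, so each criterion has an obvious home. On the literal reading, the instruction to monitor would be empty for every child without proteinuria, and a reading that voids the row's main instruction is the weaker one. This stands as evidence of intent. It does not remove the defect, because nothing in Section 7.4, the table or the SAP assigns the criteria when an event is closed.

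The second reply is that little that is mandatory is lost, and this also stands. Weekly checks are a preference, and escalation is something to consider. Section 6 allows unscheduled visits for adverse events that need repeat laboratory tests. Section 7.1 requires adverse events to be followed until they resolve or are judged permanent. Section 5.5.9 requires treatment to stop for laboratory abnormalities that the investigator judges to prevent continuing. Below age 18, a persisting fall would alert again at the next scheduled chemistry. The rationale for Amendment 4 also reports that the data monitoring committee saw no renal concern in pediatric subjects.

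Some stronger readings are tempting but not supported:

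- *A child would go unchecked for up to 16 weeks while dosing continues.* Table 6-2 chemistry visits in the extension are mostly 12 weeks apart, 16 weeks in three intervals such as Week 88 to 104, with home doses between them. But that is the schedule's floor, reached only if the investigator does nothing more, and the 16-week interval is the worst case.
- *Acute kidney injury is closed the same way.* The row for a fall of 50% or more does not make its own action depend on the footnotes. Only the general monitoring line for all renal events reaches it, and there the frequency is at the investigator's discretion.
- *Closure of hematuria and glucosuria, and resolution when baseline eGFR is 90 or below, also need new rules.* These may deserve clinical thought, but no defect of this kind has been shown for them.

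**Conclusion.** The footnotes are wrong as written, and the severity is minor. For a confirmed, persisting eGFR fall of 25 to less than 50%, literal application gives resolved at PCR below 0.2 g/g, and at least stabilized at PCR below 0.3 g/g under any grouping of footnote 3.

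The conclusion rests on two things: a site applying the connectives as printed, and the PCR being obtained as the protocol orders. It does not rest on the sponsor having meant PCR to close serum events. A reader might infer that from the wording, but Section 7.4 points the other way.

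For proteinuria with preserved eGFR, the ambiguity affects only when monitoring ends and what outcome is recorded, because that row has its own PCR trigger above 0.2 g/g. The safeguards are weakest for a subject who turns 18 during an event, since the renal procedure then no longer requires a new alert. No frequency of affected children can be derived from the documents. Efficacy analyses and hypothesis tests are not affected.

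**What to change.** In both footnotes, state that serum events resolve or stabilize on the eGFR criteria only, and that proteinuria resolves or stabilizes on the PCR criteria only. Keep the existing thresholds. PCR would still be measured in serum events, as diagnostic information and not as a closing criterion.

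The cost is a rewording of two footnotes and a memo to sites. No new assessment is needed, because eGFR and PCR are already in Table 7-1. Some events would stay open and be followed for longer, including in a few subjects past age 18.
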